## 8.2. Safety Assessments

Planned timepoints for all safety assessments are provided in the Schedule of Activities (Section 1.3).

### 8.2.1. Physical Examinations

The participant will be examined by qualified medical personnel performing a modified physical examination, which may include assessments of: general appearance; head, eyes, ears, nose, and throat; heart/cardiovascular; lungs; abdomen; neurologic; extremities; back; musculoskeletal; lymphatic; and skin. Height and weight will also be measured and recorded.

### 8.2.2. Vital Signs

Vital signs will be assessed as follows:

- Temperature, pulse rate, and BP will be assessed.
- BP and pulse measurements will be assessed with participants in a seated position with a completely automated device. Manual techniques will be used only if an automated device is not available.
- Blood pressure and pulse measurements should be preceded by at least 5 minutes of rest in a seated position.

### **8.2.3. Pregnancy Testing**

Pregnancy testing will be conducted at the Baseline Office visit. Urine pregnancy tests will be used unless the study site requires the use of serum testing, in which case serum testing will be used. WOCBP must have a negative test result before receiving study treatment. This test may also be performed at any other visit, at the investigator's discretion. At each visit, the investigator should discuss contraceptive use compliance with WOCBP females of childbearing potential (see [Appendix 7](#) for more details).

### **8.2.4. Clinical Safety Laboratory Assessments**

See [Appendix 2](#) for the list of clinical laboratory tests to be performed and the Schedule of Activities (Section [1.3](#)) for the timing and frequency.

At Screening, the investigator or qualified subinvestigator will assess the clinical significance of any values outside the reference ranges provided by the laboratory, and participants with abnormalities judged to be clinically significant will be excluded from the study.

### **8.2.5. Ocular Safety Assessments**

#### **8.2.5.1. Macroscopic Conjunctival Hyperemia Assessment**

Macroscopic conjunctival hyperemia will be assessed using the appropriate assessment guide (see the Procedure Manual for further details).

#### **8.2.5.2. Best-corrected Visual Acuity**

Visual acuity tests will be performed at all visits except on Day 1 and at the Sleep Lab visits. Manifest refraction using Snellen equivalent with a logMar chart (see Procedure Manual) will be performed at Screening, Baseline (Office visit), and Month 12/Study Exit. At all other visits, the visual acuity technician will use the last manifest refraction performed and determine the Snellen equivalent visual acuity using the logMar chart. If there is a 2-line or more reduction in visual acuity from the last best-corrected visual acuity performed, a repeat manifest refraction in both eyes and BCVA will be performed. See the Procedure Manual for further details.

#### **8.2.5.3. Visual Field**

Visual field examinations will be assessed using automated perimetry (using either Humphrey 24-2 full threshold program or 24-2 SITA Standard, or Octopus G1 or 24-2 and dynamic or normal strategy). The same test methodology must be used throughout the entire study for a given participant. If dilation is required to perform this test, then the visual field test should be performed after gonioscopy/angle assessment or with the scheduled dilated exams, if applicable. See the Procedure Manual for further details.

#### **8.2.5.4. Specular Microscopy**

Endothelial cell density will be assessed using specular microscopy performed on the central cornea. The determination of central endothelial cell density for study entry as well as study visit

measures will be by the study investigator using automated analysis. See the Procedure Manual for further details. The same instrument and analysis methodology must be used throughout the study for a given participant.

#### **8.2.5.5. Biomicroscopy**

Biomicroscopic examinations will be performed using a slit lamp. The examinations will include evaluation of the condition of the eyelids, conjunctiva, cornea, AC (with Van Herick anterior chamber depth assessment at Screening only), iris/pupil, and lens (lens assessment is performed using the modified AREDS procedure and is collected on dilated examination days through a dilated pupil, using the slit-lamp biomicroscope. Please see the Procedure Manual for details).

#### **8.2.5.6. Gonioscopy/Angle Assessment**

Gonioscopic examinations will be performed by the study investigator as described in the Procedure Manual. At Screening and the Baseline Office visits, the investigator's eligibility assessments must confirm participant eligibility for participation in the study. In subsequent gonioscopic examinations during the study, the investigator will evaluate the inferior iridocorneal angle and the Bimatoprost SR implant.

#### **8.2.5.7. Pachymetry**

Corneal thickness using ultrasound (contact) pachymetry will be performed on the central cornea. The same instrument should be used throughout the study for a given participant. Pachymetry may be performed any time after non-contact exams. See the Procedure Manual for further details.

#### **8.2.5.8. Dilated Ophthalmoscopy**

The stereoscopic fundus assessments should be conducted through a dilated pupil. The examinations will include evaluation of the macula, vitreous, and retina.

#### **8.2.5.9. Optic Disc Examination**

The cup/disc ratio and presence of optic disc pathology will be determined using stereoscopic evaluation.

### **8.3. Adverse Events and Serious Adverse Events**

The definitions of an AE or SAE can be found in [Appendix 3](#).

AEs may be reported by the participant (or, when appropriate, by a caregiver, surrogate, or the participant's legally authorized representative).

Additionally, the investigator and any qualified designees are responsible for detecting, documenting, and recording events that meet the definition of an AE or SAE and remain responsible for following up AEs that are serious, considered related to the study treatment or study procedures, or that caused the participant to discontinue the study treatment or the study (see Section 7).

### **8.3.1. Time Period and Frequency for Collecting Adverse Event and Serious Adverse Event Information**

All AEs and SAEs from the signing of the ICF until the study exit visit will be collected at the timepoints specified in the SoA (Section 1.3), and as observed or reported spontaneously by study participants.

Medical occurrences that begin before the start of study treatment, but after obtaining informed consent will be recorded in the AE section of the eCRF.

All SAEs will be recorded and reported to the sponsor or designee within 24 hours, as indicated in Appendix 3. The investigator will submit any updated SAE data to the sponsor within 24 hours of it being available.

Investigators are not obligated to actively seek AE or SAE information after conclusion of the study participation. However, if the investigator learns of any SAE, including a death, at any time after a participant has been discharged from the study, and he/she considers the event to be reasonably related to the study intervention or study participation, the investigator must promptly notify the sponsor.

The method of recording, evaluating, and assessing causality of AEs and SAEs and the procedures for completing and transmitting SAE reports are provided in Appendix 3.

### **8.3.2. Method of Detecting Adverse Events and Serious Adverse Events**

Care will be taken not to introduce bias when detecting AEs and/or SAEs. Open-ended and nonleading verbal questioning of the participant is the preferred method to inquire about AE occurrences.

### **8.3.3. Follow Up of Adverse Events and Serious Adverse Events**

After the initial AE/SAE report, the investigator is required to proactively follow each participant at subsequent visits/contacts. All AEs/SAEs will be followed until resolution, stabilization, the event is otherwise explained, or the participant is lost to follow-up (as defined in Section 7.3).

The investigator is obligated to perform or arrange for the conduct of supplemental measurements and/or evaluations as medically indicated or as requested by the sponsor or designee to elucidate the nature and/or causality of the AE or SAE as fully as possible. This may include additional laboratory tests or investigations, histopathological examinations, or consultation with other health care professionals.

If a participant dies during participation in the study or during a recognized follow-up period, the investigator will provide Allergan with a copy of any postmortem findings including histopathology.

New or updated information will be recorded in the originally completed eCRF.

The investigator will submit any updated SAE data to sponsor or designee within 24 hours of receipt of the information.

#### **8.3.4. Regulatory Reporting Requirements for Serious Adverse Events**

- Prompt notification by the investigator to the sponsor of an SAE is essential so that legal obligations and ethical responsibilities towards the safety of participants and the safety of a study intervention under clinical investigation are met.
- The sponsor has a legal responsibility to notify both the local regulatory authority and other regulatory agencies about the safety of a study intervention under clinical investigation. The sponsor will comply with country-specific regulatory requirements relating to safety reporting to the regulatory authority, IRBs/ IECs, and investigators.
- Investigator safety reports must be prepared for SUSARs according to local regulatory requirements and sponsor policy and forwarded to investigators as necessary.
- An investigator who receives an investigator safety report describing an SAE or other specific safety information (eg, summary or listing of SAEs) from the sponsor will review and then file it along with the investigator's brochure and will notify the IRB/IEC, if appropriate according to local requirements.

#### **8.3.5. Pregnancy**

- If a pregnancy is confirmed after the participant has received the study treatment, the participant may choose to exit the study after appropriate safety follow-up or to remain in the study for all safety and efficacy follow up assessments through the study exit visit.
- Details of all pregnancies in female participants will be collected from the signing of the ICF and through the duration of the pregnancy.
- If a pregnancy is reported, the investigator should inform Allergan within 24 hours of learning of the pregnancy and should follow the procedures outlined in [Appendix 7](#).
- Abnormal pregnancy outcomes (eg, spontaneous or elective abortion, fetal death, stillbirth, congenital anomalies, ectopic pregnancy) are considered SAEs.

#### **8.3.6. Medication Errors**

Medication error refers to any unintended error in the dose strength and/or administration of the study treatment as per instructions in the protocol and/or the Procedure Manual. Medication errors generally fall into the categories as follows:

- Wrong study drug
- Wrong dose strength
- Wrong route of administration
- Wrong participant (ie, not administered to the intended participant) or wrong eye
- Study medication expired

#### **8.4. Treatment of Overdose**

Not applicable.

#### **8.5. Pharmacokinetics**

Pharmacokinetic parameters are not evaluated in this study.

#### **8.6. Pharmacodynamics**

Pharmacodynamic parameters are not evaluated in this study.

#### **8.7. Genetics**

Genetics are not evaluated in this study.

#### **8.8. Biomarkers and Other Assessments**

##### **8.8.1. Anterior Segment Imaging**

At selected sites/selected participants only, anterior segment imaging may be performed using Allergan-approved instruments. Please see the Procedure Manual for further details. The participant's decision about whether to allow anterior segment imaging will not affect their eligibility for participation in the study.

#### **8.9. Health Economics**

Health economics are not evaluated in this study.

### **9. Statistical Considerations**

Two database locks are planned for this study. The first database lock, for the primary and secondary efficacy endpoint analysis, will occur when 100% of participants have completed the primary visit (ie, Week 8 Sleep Lab visit) or prematurely discontinued prior to the Week 8 Sleep Lab visit. Similarly, the second database lock for the full study database will occur after all participants have completed the study at Month 12 or prematurely discontinued from the study. Analyses will be performed after each lock: the primary and secondary efficacy analysis results are based on the first database lock, and the analyses based on the second database lock provides further efficacy and safety information. Prior to the first database lock a detailed analysis plan will be finalized.

#### **9.1. Statistical Hypotheses**

There are no statistical hypotheses for this study.

## 9.2. Sample Size Determination

The sample size is based on practical considerations. Approximately 35 participants will be enrolled: 25 to 30 in the Bimatoprost SR cohort and 5 in the LUMIGAN 0.01% cohort.

Twenty-five to 30 participants will be enrolled in the Bimatoprost SR cohort to achieve a minimum total of 20 evaluable participants, defined as participants with sufficient data at baseline and Week 8 to evaluate the 24-hour IOP-lowering effect of Bimatoprost SR. This assumes a premature discontinuation rate of up to 33%. Participants who prematurely discontinue from the study will not be replaced.

Participants will be assigned to the Bimatoprost SR or LUMIGAN 0.01% cohort by the investigator.

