#### Objectives and Endpoints:

Objectives	Endpoints/Measures

Efficacy:
 
Primary
 
 
To evaluate the 24-hour IOP-lowering effect of Bimatoprost SR in participants with OAG or OHT
 
 
Secondary
 
 
To evaluate the change in diurnal variation of IOP in eyes treated with Bimatoprost SR
 
 
Other
 
 
To evaluate the IOP-lowering effect of Bimatoprost SR
 
	
 
Time-matched IOP change from Baseline Sleep Lab visit at Week 8 Sleep Lab visit in Bimatoprost SR-treated eyes
 
Change from baseline in range of IOP in eyes treated with Bimatoprost SR at Week 8 Sleep Lab visit
 
Hour 0 IOP change from baseline through Month 12
 
Time to initial use of nonstudy IOP-lowering treatment
 

Objectives	Endpoints/Measures

Safety:
 
 
To evaluate the safety of Bimatoprost SR in participants with OAG or OHT
 
	
 
AEs, visual fields, visual acuity, macroscopic bulbar conjunctival hyperemia, slit-lamp biomicroscopic assessments, dilated ophthalmoscopic assessments (including optic disc assessment), contact ultrasound pachymetry, gonioscopy, specular microscopy
 

**Overall Study Design:** This is a multicenter, open-label, Phase 3b study in participants with OAG or OHT.

**Number of Participants:** Approximately 35 participants will be enrolled: 25 to 30 in the Bimatoprost SR cohort (to achieve a minimum total of 20 evaluable participants at baseline and Week 8 to evaluate the 24-hour IOP-lowering effect of Bimatoprost SR, assuming a premature discontinuation rate of up to 33%), and 5 in the LUMIGAN® 0.01% (bimatoprost ophthalmic solution) cohort. Participants who prematurely discontinue from the study will not be replaced.

**Number of Sites:** Approximately 3 sites in the United States

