## 4. Study Design

### 4.1. Overall Design

This is a multicenter, open-label, Phase 3b study in participants with OAG or OHT. Approximately 35 participants will be enrolled: 25 to 30 in the Bimatoprost SR cohort (to achieve a minimum total of 20 evaluable participants at baseline and Week 8 to evaluate the 24-hour IOP-lowering effect of Bimatoprost SR, assuming a premature discontinuation rate of up to 33%), and 5 in the LUMIGAN 0.01% cohort. Participants who prematurely discontinue from the study will not be replaced.

Participants in the Bimatoprost SR cohort will receive a 10 µg implant in the study eye on Day 1, and the fellow eye will receive standard of care treatment (provided that there is no known crossover effect of the fellow eye's standard of care treatment to the study eye) for the duration of the study (see Sections 6.5.2 and 6.5.4 for additional details). At selected site(s) an additional cohort of participants will be enrolled and assigned to receive topical LUMIGAN 0.01% in the study eye (once daily, at 20:00 ± 1 hour, starting with the evening dose on Day 1), and standard of care treatment in the fellow eye (provided that there is no known crossover effect of the fellow eye's standard of care treatment to the study eye) for the duration of the study. Participants will be assigned to the Bimatoprost SR cohort or LUMIGAN 0.01% cohort [REDACTED].

The participant and investigator will not be masked to the study treatment assignment for the duration of the study. Site staff collecting 24-hour IOP measurements at Sleep Lab visits will be masked to the study treatment and study eye.

Study Eye Treatment	Fellow Eye Treatment
Bimatoprost SR 10 µg or LUMIGAN 0.01% a (at selected site[s])	Standard of Care

a Participants will begin self-administration of LUMIGAN 0.01% in the study eye once daily in the evening (20:00 ± 1 hour) starting with the evening dose on Day 1, and will continue self-administration daily through the duration of the study.

The duration of the study for each participant is approximately 15 months, consisting of a screening period of up to 60 days before washout; washout period of up to 42 days before Baseline; and 12 months of follow-up.

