#### **4.4. End of Study Definition**

The end of the study is defined as the date of the last visit of the last participant in the study or last scheduled procedure shown in the SoA for the last participant in the study.

A participant assigned and treated with Bimatoprost SR is considered to have completed the study if he/she has completed all visits of the study to Month 12. At the Month 12/Study Exit visit, if the investigator determines that any safety concerns warrant participant follow-up, the participant may be followed post exit until safety concerns are resolved based on the investigator's discretion. Participants assigned and treated with LUMIGAN 0.01% may early exit the study after completion of the Week 8 Sleep Lab visit, if there are no safety concerns in the opinion of the investigator, and at which time all assessments performed at the Month 12/Study Exit visit should be performed.

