## 7. Discontinuation of Study Intervention and Participant Discontinuation/Withdrawal

A premature discontinuation from study treatment will occur if a participant who signs the ICF and receives study treatment ceases participation in the study, regardless of circumstances, before the completion of the protocol-defined study procedures.

Notification of early participant discontinuation from the study and the reason for discontinuation will be made to the sponsor and will be clearly documented on the appropriate eCRF.

Reasons for discontinuation from the study treatment and/or the study may include the following commonly used or other acceptable terms:

Commonly Used Terms	Other Acceptable Terms
Adverse event Completed Lack of efficacy Lost to follow-up Noncompliance with study drug Other Physician decision Pregnancy Protocol deviation Screen failure Site terminated by sponsor Study terminated by sponsor Withdrawal by subject	Death Failure to meet enrollment criteria Progressive disease Technical problems

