### 10.6. Appendix 6: Study Tabular Summary

This table is intended for use in posting study information to registries (eg, ClinicalTrials.gov).

Parameter Group	Parameter	Value
Trial information	Trial Title	An Evaluation of the 24-Hour IOP-lowering Effect of Bimatoprost SR in Participants with Open-Angle Glaucoma or Ocular Hypertension
	Clinical Study Sponsor	Allergan Sales LLC
	Trial Phase Classification	Phase 3b Trial
	Trial Indication	Open-angle glaucoma or ocular hypertension
	Trial Indication Type	Treatment
	Trial Type	Efficacy Safety
	Trial Length	15 months
	Planned Country of Investigational Sites	United States
	Planned Number of Subjects	30
	FDA-regulated Device Study	No
	FDA-regulated Drug Study	Yes
	Pediatric Study	No
Subject information	Diagnosis Group	Open-angle glaucoma or ocular hypertension
	Healthy Subject Indicator	No
	Planned Minimum Age of Subjects	18
	Planned Maximum Age of Subjects	Not specified
	Sex of Participants	Both
	Stable Disease Minimum Duration	Not specified

Parameter Group	Parameter	Value	
Treatments	Investigational Therapy or Treatment	Bimatoprost SR	LUMIGAN 0.01%
	Intervention Type	Drug	Drug
	Pharmacological Class of Investigational Therapy	Prostaglandin analog	Prostaglandin analog
	Dose Strength per Administration	10 µg	0.01%
	Dose Units	1 implant	Drop
	Dosing Frequency	Single dose	Once daily in the evening
	Route of Administration	Intracameral	Topical ophthalmic
	Current Therapy or Treatment	No	No
	Added on to Existing Treatments	No	No
	Control Type	None	None
	Comparative Treatment Name	N/A	N/A
Trial design	Study Type	Interventional	
	Intervention Model	2 arm	
	Planned Number of Arms	2	
	Trial is Randomized	No	
	Randomization Quotient	N/A	
	Trial Blinding Schema	Open-label	
	Stratification Factor	N/A	
	Adaptive Design	No	
Study Stop Rules	None		

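### At the stated 33% loss, if it falls by Week 8, enrolling 25 to 28 Bimatoprost SR participants misses the plan's minimum of 20 evaluable; 25 is enough only if loss is 20% or less

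*Protocol*

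**What the plan says.** Protocol 9.2 gives the size of the Bimatoprost SR cohort: "Twenty-five to 30 participants will be enrolled in the Bimatoprost SR cohort to achieve a minimum total of 20 evaluable participants". Evaluable means having enough data at baseline and Week 8 to assess the 24-hour effect. The same paragraph adds "This assumes a premature discontinuation rate of up to 33"% and says that participants who discontinue are not replaced. SAP 3 repeats this. The Synopsis (Protocol 1.1), Protocol 4.1 and SAP 1.2 give the same numbers; Protocol 4.1, for example, has "to achieve a minimum total of 20 evaluable participants at baseline and Week 8".

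One loss rate is attached to the whole range of 25 to 30. No time point is attached to that rate. Protocol 7 defines premature discontinuation as occurring when a treated participant "ceases participation in the study, regardless of circumstances, before the completion of the protocol-defined study procedures". Under Protocol 4.4, an SR participant is "considered to have completed the study if he/she has completed all visits of the study to Month 12".

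**The concern.** Twenty is the only target the plan sets for evaluable participants, and it is called a minimum. A minimum should hold at the worst loss the plan allows for, at every enrolment the plan permits. If 33% is the loss by Week 8, a site team that stops at 25 has followed the protocol and should still expect to miss the minimum, and the no-replacement rule leaves no remedy.

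The timing is a second gap. Evaluability is settled at Week 8, but discontinuation as defined runs to Month 12. The reader cannot tell how much of the 33% is meant to fall before the visit that matters.

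What is at stake is precision and a clear size rationale. The primary result is a set of mean time-matched changes at 12 timepoints, each with a paired-t 95% confidence interval (SAP 5.3.2). Fewer evaluable participants widen those intervals.

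**Working it through.** **Inputs.** All from Protocol 9.2 and SAP 3: minimum evaluable 20; SR enrolment N = 25 to 30; loss d up to 0.33; no replacement. For steps 1 to 3, assume that d is the loss by Week 8.

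**1. Reproducing the plan's figure.** N = 20/(1 − d) = 20/0.67 = 29.85, rounded up to 30. This is the top of the stated range. The bottom does not reproduce at 33%. It reproduces at 20% loss: 20/(1 − 0.20) = 25.

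**2. Evaluable participants across the range.** Expected number = N × 0.67. Whole-person count = N − floor(0.33 × N), which treats 33% as a cap on the losses that occur. Largest tolerable loss = (N − 20)/N.

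| Enrolled | Expected at 33% loss | Whole persons left | Largest loss leaving 20 |
|---|---|---|---|
| 25 | 16.75 | 17 | 5 (20.0%) |
| 26 | 17.42 | 18 | 6 (23.1%) |
| 27 | 18.09 | 19 | 7 (25.9%) |
| 28 | 18.76 | 19 | 8 (28.6%) |
| 29 | 19.43 | 20 | 9 (31.0%) |
| 30 | 20.10 | 21 | 10 (33.3%) |

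Enrolments of 25 to 28 fall short on both counts. Twenty-nine falls short on expectation and reaches 20 only in whole persons. Thirty meets the target on both.

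**3. Sensitivity at 25 enrolled.** The documents give no Week 8 loss rate, so this range is an assumption: 10% leaves 22.5, 15% leaves 21.25, 20% leaves 20, 33% leaves 16.75.

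**4. If 33% is a 12-month rate instead.** With 25 enrolled, 25 × 0.33 = 8.25 losses are expected over the study. Twenty remain evaluable only if at most 5 of them (5/8.25 = 61%) occur before the Week 8 Sleep Lab visit. The plan states no such split.

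**5. Effect on precision.** The 95% half-width in SD units is t(0.975, n − 1)/√n:

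- n = 20: 0.468
- n = 19: 0.482 (3% wider)
- n = 18: 0.497 (6% wider)
- n = 17: 0.514 (10% wider)

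**The case against.** The strongest reply is that a range of enrolment has been set against a range of loss. A rate of up to 33% is a ceiling, and the ceiling pairs naturally with 30. Twenty-five pairs with 20%, which also lies under the ceiling. On that reading no number is wrong, and the shortfall comes from combining the lowest enrolment with the highest loss. The text does not state that pairing, however. It applies a single rate to the whole range and calls 20 a minimum, so 25 remains a permitted enrolment that fails at the stated ceiling.

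The second reply is about timing, and it stands as a limit on the finding. The definition in Protocol 7 covers the whole study. Section 9 of the Protocol names the Week 8 Sleep Lab visit explicitly when it means discontinuation before that visit; the sample-size paragraph does not. A participant who leaves after that visit is still evaluable. Loss by Week 8 could therefore be well under 33%, and 25 could be enough. But the 33% directly follows the Week 8 definition of evaluable, so the Week 8 reading is also natural.

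Third, about 35 in total with 5 on LUMIGAN already points to 30 SR participants. This is correct and makes the fix easy, but it does not remove the explicit lower limit of 25.

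Fourth, the size is described as practical, there are no hypotheses, and no decision depends on reaching 20. This limits the impact and is granted.

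**Conclusion.** The concern holds in its conditional form. If the stated 33% loss occurs by Week 8, enrolling 25 to 28 SR participants leaves 17 to 19 evaluable at best (16.75 to 18.76 expected), below the stated minimum of 20. Thirty are needed by the usual inflation formula, or 29 if losses are whole persons capped at 33%. Twenty-five is enough only at 20% loss or less, and no section states that rate. If 33% is a 12-month figure, 25 may be adequate, but only with a split of losses that the plan does not give.

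The impact is modest: intervals up to about 10% wider at the same SD, with no test or power claim affected. Evaluable numbers could fall further, because IOP taken after rescue is excluded from the full analysis set (Protocol 9.3, SAP 4.2) and the discontinuation rate does not cover that. No rescue rate by Week 8 is given, so no size is claimed for it. The point should be fixed because the plan's own figures disagree and the correction is simple.

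**What to change.** Reword the sample-size statement in either of two ways:

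- Keep the range and state what each end tolerates: at least 20 evaluable participants are expected with up to 33% loss before Week 8 if 30 are enrolled, and with up to 20% loss if 25 are enrolled.
- Or name 30 as the SR target, which is inside the planned range and agrees with a total of about 35.

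In either case, define the loss as having no usable Week 8 Sleep Lab IOP. If 33% was meant as a Month 12 rate, say so and give the rate assumed by Week 8.

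The text to change is in Protocol 1.1, 4.1 and 9.2 and SAP 1.2 and 3. No participants beyond the planned range are needed. Protocol edits mean an amendment, and Protocol 10.1.1 requires IRB/IEC approval before design changes are implemented. The first option only clarifies and is the lighter one, although it makes visible that 25 enrolled tolerates only 20% loss.

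A separate clerical point can be corrected at the same time: Protocol Appendix 6 lists "Planned Number of Subjects 30" in a table covering both arms, against about 35 elsewhere. It has no bearing on the argument above.
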